15.0 Compensation for Research-Related Injury

15.1 Compensation for Research-Related Injury: N/A

15.2 Contract Language: N/A

16.0 Consent Process

16.1 Consent Process (when consent will be obtained): Once subjects are removed from sedation and able to follow 3/3 one-step commands.

- Consent will occur in the hospital room of the subject. There will be no waiting period between initial consent and initiation of study.
- Ongoing verbal consent to activity will be addressed daily, when the therapist approaches a subject for scheduled therapy.
- Consent will be obtained via pre-approved form.

16.2 Non English-Speaking Participants: Any non-English speaking individual who is being treated by a physical therapist and who is undergoing ECMO treatment would be eligible for consent. As advised by IRB, a line on the consent form indicating who facilitated consent in the case of a non-English speaker, has been added.

PROTOCOL TITLE: The Impact of Lower Extremity Weight-Bearing Leg Exercise During the Pre-Ambulation Phase of Individuals Undergoing Extracorporeal Membrane Oxygenation (ECMO)
VERSION DATE: 11/28/16

16.3 Participants Who Are Not Yet Adults (infants, children, teenagers under 18 years of age): N/A

16.4 Cognitively Impaired Adults, or adults with fluctuating or diminished capacity to consent: N/A

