Aim 1: To determine if closed-chain leg exercise decreases the time to initial ambulation. *We hypothesize* that adding leg exercise will decrease time to ambulation.

Aim 2: To determine the impact of closed chain leg exercise on functional ability. *We hypothesize* that adding leg exercise will improve functional outcomes when added to an existing early mobilization program.

Aim 3: To determine the effect of closed chain leg exercise on hospital outcomes. *We hypothesize* that hospital related outcomes will improve when leg exercise is added to an existing early mobilization program.

Research Design & Methods

This initial pilot study will be conducted at the University of Minnesota Medical Center (UMMC), Fairview, and will involve 10 participants in each of the two groups (A and B). To account for attrition, 24 total subjects will be recruited; 12 per group. Approximately 3-5 patients are admitted to UMMC each month who are undergoing ECMO and could be considered for study inclusion. The study will be conducted with a goal endpoint of 1-year. Men and women aged 18-70 years old with refractory respiratory failure who are undergoing ECMO will participate over the duration of their ECMO treatment and hospitalization.

Recruitment and Consent

Standard practice includes a physician order for inpatient physical therapy for all individuals undergoing ECMO, as well as initial medical sedation. Most of those receiving ECMO are at least partially medically sedated at the time of physical therapy initiation. Only physical therapists who are specialty-trained ICU therapists and who are a part of this project will be working with this group of patients.

Any individual who meets inclusion criteria will be considered for participation, pending their ability to follow 3/3 one-step commands, as is outlined in the ECMO Mobility Protocol listed previously. Patients will be able to self-consent once sedation is reduced. After consent, individuals will be placed into either Group A or B and progress through the protocol. Group assignments will be determined based on 24 subjects, with the number 24 put into a random letter sequence generator prior to subject recruitment.

Inclusion Criteria

- Men and women 18-70 years old with refractory respiratory failure undergoing ECMO at the University of Minnesota Medical Center, Fairview.
- Able to follow 3 out of 3 one-step commands via protocol.
- Active Inpatient Physical Therapy Referral.

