- ECMO delivery is veno-venous with internal jugular catheter.

Exclusion Criteria

- Femoral catheter of any kind present.
- Veno-arterial ECMO setup.
- Sedation such that self-consent is not attainable.
- Medical instability, as determined by primary critical care physician.

Overview of Protocol for Aims 1-3:

Participants in either Group A (closed chain leg exercise group) or B (open chain exercise group) will progress through the established ECMO protocol led by their physical therapist. Participating therapists have extensive experience in working with patients on the Moveo who are in the ICU. Subjects will be assisted in the supine position from their bed to the Moveo device via a lateral transfer across a slide board to facilitate ease of movement.

Those in Group A will participate in leg exercise on the Moveo during item 4d of the ECMO protocol, whereby those in Group B will complete standard exercise as listed in item 4d. Group A participants will use the Moveo until subjective report of leg fatigue. Participants will self-select the pace of their leg exercise and the primary therapist will determine guidelines for percent of body weight lifted in accordance with standard practice physical therapy. Subjects will complete 1-4 sets of up to 25 reps of the squat exercise with 2 minutes of rest between each set. Subjects will receive physical therapy 5 days/week regardless of randomization into Group A or Group B.

Data Collection for Aims 1-3: Data will be collected on Day 0 (physical therapy evaluation day), Day 5, Day 10, Day 15, Day 20, Day 30, Day 45 (if applicable), and Day of discharge. Data collected will be categorized as specific to Aim 1 (time from initial physical therapy evaluation to initial ambulation), Aim 2 (functional outcomes) and Aim 3 (hospital outcomes). Recording of physiological data including heart rate (HR), blood pressure (BP), oxygen saturation (O2), and respiratory rate (RR) will be completed by trained physical therapists involved in the protocol at the onset of, and 1-minute post-conclusion of each therapy session. Therapy sessions are to be delivered at a frequency of five sessions per week.

- Functional Outcomes

- Leg strength as assessed by primary therapist via manual muscle test, using the Medical Research Council Sum Score (MRC Score)
- Grip strength, as assessed by hand dynamometer, completed by primary therapist

- 30-second sit to stand, completed by primary therapist

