 - Richmond Agitation and Sedation Scale (RASS), as completed in medical record by primary nurse
 - Functional Status Score for the Intensive Care Unit (FSS-ICU)
- Hospital Outcomes (data extraction from medical record)
 - Hospital days
 - Intensive care unit days
 - Days on ECMO
 - Days on mechanical ventilation
 - Length of time from physical therapy evaluation to initial ambulation
 - Discharge disposition- assigned a number for statistical analysis
 - Home (1)
 - Home with assistance (2)
 - Home with home therapy (3)
 - Home with outpatient therapy (4)
 - Transitional Care Unit (5)
 - Acute Inpatient Rehabilitation (6)
 - Long-term acute care hospital (7)
 - Long-term care setting (8)
 - Transfer to outside hospital (9)
- Physiological Monitoring: Monitoring physical therapists have extensive experience in mobilizing patients in the ICU, including those with arterial lines and on ventilation, as is standard practice for ICU therapy.
 - Respiratory rate (RR) via Drager Ventilators
 - Evita Series or Infinity Series
 - Oxygen (SpO2) and heart rate (HR)
 - Spacelabs Ultraview SL2700 (regular monitor)
 - Spacelabs Ultraview SL (portable monitor)
 - Blood Pressure (BP) via manual cuff or arterial line
 - Spacelabs Ultraview SL2700 or SL

Statistical Considerations

Physiological data (HR, BP, O2, RR) will be recorded throughout the study and analyzed between Groups A and B. Functional and Hospital outcomes will be analyzed to compare group differences at each of the data collection days (0, 5, 10, 15, 20, 30, 45, day of discharge).

Data will be analyzed at the University of Minnesota using the Statistical Package for Social Sciences (SPSS) software program. Test for normality will be completed via a paired t-test for parametric data and via Wilcoxon Rank Sum Test for non-parametric data.

Aim 1: Leg exercise on the Moveo will decrease time to initial ambulation.

- A paired t-test will be used to evaluate time to ambulation in Group A as compared to Group B.

Aim 2: Leg exercise on the Moveo will improve functional outcomes.

- There are 2 primary factors to assess, Group A and B, as well as the impact across time. To assess both factors, repeated measures ANOVA will be used.

Aim 3: Leg exercise on the Moveo will improve hospital outcomes.

- All hospital outcomes, except for discharge disposition, can be assessed between Group A and Group B by a paired t-test.
- Discharge disposition, categorical data, will be analyzed via Chi-Square test.

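### Aim 2's repeated-measures ANOVA does not name the term that tests Moveo: the time effect cannot test it, and the group effect is a valid test diluted by Day 0

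*Combined protocol and SAP*

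**What the plan says.** The Aim 2 hypothesis (Specific Aims) is that "adding leg exercise will improve functional outcomes when added to an existing early mobilization program". The analysis for it, under Statistical Considerations, is two sentences. The first sets out what is to be assessed: "There are 2 primary factors to assess, Group A and B, as well as the impact across time". The second gives the method and nothing more: "To assess both factors, repeated measures ANOVA will be used". No interaction, contrast, covariate, primary day or deciding term is given.

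The same section also states: "Functional and Hospital outcomes will be analyzed to compare group differences at each of the data collection days", listing Day 0 to day of discharge.

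Four other places fix what Day 0 is:

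- The visit schedule (under Data Collection for Aims 1-3) reads "Data will be collected on Day 0 (physical therapy evaluation day), Day 5, Day 10, Day 15, Day 20, Day 30, Day 45". The last of these is conditional, and a discharge visit is added. Day 0 is therefore a level of the time factor.
- Recruitment and Consent: "Most of those receiving ECMO are at least partially medically sedated at the time of physical therapy initiation". Group placement follows consent.
- Section 16.1: consent is taken "Once subjects are removed from sedation and able to follow 3/3 one-step commands".
- Overview of Protocol for Aims 1-3: "Those in Group A will participate in leg exercise on the Moveo during item 4d of the ECMO protocol". That item comes after the command-following step in the mobilization list.

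**The concern.** A two-group repeated-measures ANOVA returns three tests: group, time, and group by time. The plan names two factors and does not say which result answers Aim 2.

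The choice matters because the terms answer different questions. The time effect asks whether patients change on average over both arms. Both arms receive physical therapy five days a week under the same mobilization protocol, so it would be expected to be positive with or without Moveo. The group effect asks whether the arms differ on average over all days, including a day on which most patients have not yet been allocated.

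Two things are at stake. A real benefit may be missed on a diluted term. And with five functional outcomes, three ANOVA terms each and a further comparison on each day, the deciding test could be picked after the results are seen.

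**Working it through.** **Plan's own figures.** The documents give 10 evaluable and 12 recruited per group (2 × 12 = 24). They give no effect size, SD, correlation, alpha or power, so there is no power statement to reproduce. Everything below except n = 10 and the visit days is an assumption.

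**Is Day 0 before treatment?** Day 0 is the therapy evaluation. Most patients are then at least partly sedated. Consent waits for three of three commands, placement follows consent, and Moveo comes at a later step. So for most patients Day 0 cannot carry a Moveo effect, and for slow wakers Day 5 may not either.

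**Assumed setting.** 10 per arm; complete data at Days 0, 5, 10, 15, 20; SD 1; full benefit 1 SD; exchangeable correlation ρ = 0.5; two-sided alpha 0.05. There are three shapes of benefit: linear build to Day 20 (0, 0.25, 0.5, 0.75, 1), full from Day 5 (0, 1, 1, 1, 1), and full from Day 10 (0, 0, 1, 1, 1).

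**Group effect** (equal-weight mean of five days)

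- Benefit kept: 2.5/5 = 0.50 linear; 4/5 = 0.80 from Day 5; 3/5 = 0.60 from Day 10.
- Variance of a patient's mean = (1 + 4ρ)/5 = 0.60. SE of the difference = √(2 × 0.60/10) = 0.346.
- Noncentrality 0.50/0.346 = 1.44, 0.80/0.346 = 2.31, 0.60/0.346 = 1.73. Power on 18 df: 0.28, 0.59, 0.37.

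Day 0 alone accounts for a factor of 4/5 in every shape. The rest of the loss in the linear and Day 10 cases comes from later days before the benefit is full.

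**Day 0-adjusted post-baseline mean** (Days 5 to 20, Day 0 as covariate)

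- Effect: 2.5/4 = 0.625; 4/4 = 1; 3/4 = 0.75.
- Variance of the four-day mean = (1 + 3ρ)/4 = 0.625. After adjustment, 0.625 − ρ² = 0.375. Estimating the covariate slope inflates this by about 1 + 1/16.
- SE = √(2 × 0.375 × 1.0625/10) = 0.282. Noncentrality 2.21, 3.54, 2.66. Power on 17 df: 0.55, 0.92, 0.71.

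**Group by time** (omnibus, F on 4 and 72 df). λ = (10/2) × Σ(effect − mean effect)²/(1 − ρ) = 6.25, 8.0, 12.0.

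**Power side by side at ρ = 0.5**

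| Shape | Group effect | Group by time | Linear slope contrast | Day 20, unadjusted | Day 0-adjusted post-baseline mean |
|---|---|---|---|---|---|
| Linear build | 0.28 | 0.46 | 0.66 | 0.56 | 0.55 |
| Full from Day 5 | 0.59 | 0.57 | 0.47 | 0.56 | 0.92 |
| Full from Day 10 | 0.37 | 0.77 | 0.81 | 0.56 | 0.71 |

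A Day 0-adjusted difference at Day 20 has power of about 0.66 in all three shapes, since each reaches 1 SD by then.

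**Other correlations.** The adjusted post-baseline mean beat the group effect in every setting tried. Adjusted against group effect, in the order linear, Day 5, Day 10:

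- ρ = 0.3: 0.54 v 0.36, 0.91 v 0.72, 0.70 v 0.48
- ρ = 0.7: 0.67 v 0.23, 0.97 v 0.49, 0.82 v 0.31
- autoregressive 0.8: 0.50 v 0.24, 0.88 v 0.51, 0.65 v 0.32

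**All eight visits.** Placing discharge at day 60, the group effect keeps 87.5% of the benefit if full from Day 5, 75% from Day 10, 58% if linear to Day 30 and 39% if linear to the last visit.

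**Time effect.** In simulation with no Moveo effect and 1 SD recovery in both arms, it was significant in 98 to 100% of trials. That rate follows from the assumed recovery. The structural point, that the term pools the arms, needs no simulation.

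**Per-day comparisons.** Eight tests at 0.05 give 1 − 0.95⁸ = 0.34 for at least one false positive per outcome if independent. Visits are correlated, so this is an upper-end illustration.

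**The case against.** Three stronger readings are tempting, and the documents do not support them.

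- A reader might infer that the plan restricts Aim 2 to main effects. It says factors, not main effects. The usual full-factorial model for two factors also yields the interaction, and nothing excludes it. The term is unspecified, not ruled out.
- A reader might infer that neither term bears on Moveo, or that natural recovery will be reported as a Moveo benefit. Under randomization the group effect moves in the right direction when the benefit is real, and it can beat the interaction: with eight visits, ρ = 0.3 and benefit from Day 5, power is 0.84 against 0.37. Nothing in the plan says the time effect will be read as proof.
- A reader might infer that the slope interaction must be the sole test. It does best in the linear and Day 10 cases above, but with full benefit from Day 5 it falls below the group effect: 0.36 v 0.72 at ρ = 0.3, and 0.33 v 0.51 at autoregressive 0.8. The documents give no trajectory to choose by.

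The best defence is that group comparisons at each collection day are already planned. The unadjusted Day 20 test has power 0.56 in the assumed setting, twice that of the group effect under linear build. This stands in part: the question is covered, but by eight candidate tests per outcome with no deciding day, no Day 0 adjustment and no multiplicity rule. It is also fair that this is a 20-patient exploratory pilot. That limits what is at stake, but the remedy is cheap.

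**Conclusion.** The concern holds in a limited form, as a change that should be made. Aim 2 does not name the term that tests Moveo. Of the two factors it does name, time cannot test it, and group tests it with dilution because Day 0 is averaged in.

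Over Days 0 to 20 the group effect keeps 50% of a 1 SD benefit that builds linearly and 80% of one that is full from Day 5. At ρ = 0.5, moving Day 0 from a time level to a covariate and comparing post-baseline means raises power from 0.28 to 0.55 and from 0.59 to 0.92. These sizes rest on assumed effect, shape, correlation and complete data. The direction of the gain over the group effect held in all settings tried, but the ranking against the interaction and slope tests did not.

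**What to change.** Replace the sentence "To assess both factors, repeated measures ANOVA will be used" with:

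> Aim 2 is decided by one pre-specified between-group contrast per functional outcome: the Group A minus Group B difference over the fixed post-baseline days (or at one named day), with the Day 0 value as a covariate and not as a level of the time factor. The group-by-time interaction and the per-day comparisons are supportive. The time main effect is not evidence for Moveo.

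List the fixed days, or the single day, before data are seen. State that the Day 0 value is taken before any Moveo session, because section 16.1 allows the study to start directly after consent. Do not make the linear slope contrast the sole test.

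**Cost.** A short change of text, with the same data and software, and one degree of freedom (18 to 17). If Day 0 scores sit at floor in sedated patients, the adjustment gains little. In the limit where Day 0 is unrelated to later scores, the variance stays at 0.625, the SE is √(2 × 0.625 × 1.0625/10) = 0.364, and power is 0.37, 0.74 and 0.49 for the three shapes, against 0.39, 0.76 and 0.52 without the covariate.

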Collecting and analyzing data on weight-bearing lower extremity exercise in this patient population will allow us to obtain important information on ways to address weakness associated with ECMO treatment, particularly in those who are unable to engage in bipedal ambulation.

[figure not shown]
MOVEO XP Mobile Hi-Lo Platform System

Company Website:

<http://www.djoglobal.com/products/charlottesville/moveo-xp>

ECMO Early Mobilization Protocol:

1. **Readiness for Mobility Assessment and Protocol** (Developed by ECMO therapy specialists at the University of Minnesota Medical Center)
 - a. Passive range of motion (PROM) and monitor for appropriateness of entering into the mobility program
 - b. Utilization of lift equipment to sit patient at the edge of the bed or into chair to promote wakefulness, when on minimal amounts or no sedation
 - c. Patient demonstrates the ability to follow 3/3 one-step commands
 - d. Patient tolerates 5 minutes of lower extremity ergometer, or performs ten reps of 3 active ROM of motion exercises involving the lower extremities
 - e. Sit at bedside unsupported for 5 minutes
 - f. Sit->stand and pre-gait activities (weight shifting, walking in place, etc.) directed by therapist
 - g. Bed->chair transfers (stand-pivot or squat-pivot)
 - h. Walking over ground with utilization of the mobility carts

The primary aim of this study is to assess the functional impact of leg exercise during the pre-ambulation phase in patients undergoing ECMO. Outcome measures will be categorized as either functional or hospital based. Hospital measures include: Hospital days, intensive care unit days, days on ECMO, days on mechanical ventilation, length of time from physical therapy evaluation to initial ambulation, and discharge disposition. Functional outcome measures include: Leg strength, grip strength, 30-second sit to stand test, Functional Status Score for the Intensive Care Unit (FSS-ICU), and the Richmond Agitation and Sedation Scale (RASS).

Background & Significance

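### Aim 2's repeated-measures ANOVA has no stated time levels; if the listed collection days are the levels, its standard form discards every patient without a Day 45 value

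*Combined protocol and SAP*

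**What the plan says.** The Aim 2 bullet in Statistical Considerations names two factors, group and time, and then the test: "To assess both factors, repeated measures ANOVA will be used". It does not say which days make up the time factor. A general sentence earlier in that section says that functional and hospital outcomes will be compared between groups "at each of the data collection days (0, 5, 10, 15, 20, 30, 45, day of discharge". Data Collection for Aims 1-3 gives the same schedule and ends it with "Day 45 (if applicable), and Day of discharge".

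Under Research Design & Methods, patients "will participate over the duration of their ECMO treatment and hospitalization"; no visit after discharge is listed. Specific Aims, Aim 3, hypothesises that "hospital related outcomes will improve when leg exercise is added to an existing early mobilization program", and the Project Summary counts length of stay among these: "Hospital measures include: Hospital days, intensive care unit days, days on ECMO".

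The plan gives no rule for incomplete patients and no imputation method, and it does not mention a mixed model. One sentence, at the end of Stopping Rules, allows data collected before a withdrawal to be used. SPSS is named as the software, without a procedure.

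**The concern.** Standard repeated-measures ANOVA needs a value from each patient at every level entered. A patient who goes home on Day 25 has no Day 30 or Day 45 value by design. That patient's Day 0 to Day 20 measurements would then leave the analysis too. The discharge score does not help: it would be a separate level, taken at a different time for each patient, and the Day 45 cell stays empty.

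Two things are at stake. The first is precision, in a pilot that plans 10 patients per group. The second is the randomised comparison itself. Still being in hospital at Day 45 is decided after randomisation, and Aim 3 expects the exercise to improve hospital outcomes. If leaving is related to function, the analysed set may differ between groups for reasons connected with the outcome.

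**Working it through.** **The plan's own numbers.** Planned size is 20 (10 per group), recruited 24 (12 per group). The allowance is 4/24 = 16.7%. The documents describe it as covering attrition and do not mention early discharge. No other figure in the plan bears on this point, so the rest is illustration under stated assumptions.

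**Mechanism.** In one simulated trial (24 patients, the seven fixed days, stay = 5 days + exponential with mean 33 days), 124 values were observed. Only 6 patients were complete, so a complete-case analysis keeps 6 × 7 = 42 values and loses 82. A mixed model used all 124 values from all 24 patients.

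**How many patients remain.** Assume a lognormal stay with log-SD 0.6. Expected patients complete to day L = 24 × [1 − Φ(ln(L/median)/0.6)].

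| Assumed median stay | Complete to Day 30 | Complete to Day 45 |
|---|---|---|
| 20 days | 6.0 | 2.1 |
| 45 days | 18.0 | 12.0 |
| 60 days | 21.0 | 16.4 |
| 90 days | 23.2 | 21.0 |

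Keeping the planned 20 requires 20/24 = 83% of patients to have a Day 45 value. If each patient independently has one with probability 75%, the chance that both groups keep 10 is 15%; at 90% it is 79%. With eight levels and two groups, the multivariate within-patient test needs N − 2 − 7 + 1 ≥ 1, so at least 9 complete patients. The chance of fewer than 9 is 88% if 25% of patients have a Day 45 value, and 8% if 50% do.

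**Whether the estimate is biased.** Assumptions: 10 patients per arm, baseline mean 5 (SD 4), gain of 0.6 against 0.4 points per day (SD 0.25), and discharge when function reaches 25. The Day 20 difference is 20 × (0.6 − 0.4) = 4.0, or 3.7 if discharged patients are held at the threshold.

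| Last level entered | Patients left of 20 | Day 20 difference, discharge at the threshold | Day 20 difference, same stays unlinked from function within arm |
|---|---|---|---|
| Day 20 | 18.6 | 3.1 to 3.2 | about 4.0 |
| Day 30 | 14.2 | 1.8 to 1.9 | about 4.0 |
| Day 45 | 8.5 | about 0.9 | about 4.0 |

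Ranges show the spread between repeated simulations. In the threshold case with Day 45 last, about 2.8 exercise and 5.7 comparison patients remain. The attenuation therefore comes from the assumed link between function and discharge, not from the loss of patients alone.

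**Direction.** In the threshold case with Day 30 last, also losing the two lowest scorers of one arm (through death, transfer or withdrawal) moves the result to about 4.0 if they are in the exercise arm, or −0.2 if they are in the comparison arm.

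**The case against.** The strongest reply is that the Day 45 deletion is inferred. The Aim 2 bullet names no levels. The list of days sits in a general sentence that also covers hospital outcomes such as disposition, which have a single value and cannot form eight levels. The conditional wording for Day 45 shows that the authors expected some patients to lack it. This stands, and it limits confidence in the specific Day 45 claim. But no other set of days is given for functional outcomes, and a Day 0-to-discharge version would confound time with length of stay.

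It can also be said that the plan means to use partial data. A comparison at each day could use whoever is present, and data collected before withdrawal may be kept. Neither changes the Aim 2 test. The withdrawal sentence does not cover discharge and gives no method. SPSS can fit mixed models, but the plan names a different test.

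A reader might go further and infer that the plan excludes early-discharged patients by rule, that most patients will be lost, or that a true benefit will be diluted. The documents support none of these. There is no exclusion rule. Without length-of-stay data, the loss could be small if stays are long. Dilution appears only when discharge follows function; the listed dispositions include long-term acute care and transfer to another hospital, so leaving is not always recovery.

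**Conclusion.** The concern holds in a conditional form. Aim 2 is assigned a test whose standard form does not use incomplete patients (high confidence), in a study where follow-up ends at discharge and no rule for incomplete patients is given. If the listed days are the levels, every patient without a Day 45 value is dropped, earlier values included (moderate confidence, because the levels are not stated).

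The loss is certain in kind but not in size: about 2 to 21 of 24 patients complete to Day 45 and 6 to 23 to Day 30, under a lognormal stay with log-SD 0.6 and an assumed median of 20 to 90 days. If patients leave before Day 45, lost precision is the sure harm. Bias is plausible because the exercise is expected to improve hospital outcomes, but it depends on how leaving relates to function, and its net direction is uncertain. This should be fixed before analysis; the collected data remain usable.

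**What to change.** Replace repeated-measures ANOVA for Aim 2 with a linear mixed model (SPSS MIXED, REML, small-sample degrees of freedom) on all available scheduled-day assessments of all randomised patients. Terms: group, categorical day (0, 5, 10, 15, 20, 30, 45), group-by-day, and a random intercept per patient, with a random slope for day if it converges. Do not enter day of discharge as a time level; report that comparison separately as descriptive.

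Base the Aim 2 conclusion on days up to about Day 15, where most patients are expected to be present, and treat later days as exploratory. In simulations with equal slopes at a nominal 5% level, the random-intercept model rejected in 2.0%, 4.0% and 7.4% of trials at Days 10, 15 and 20; with a random slope it was 3.8%, 3.9% and 4.4%. Those runs also placed discharge scores on the nearest scheduled day; a check on scheduled days alone showed the same pattern for the random intercept.

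Using discharge scores inside the model is optional and needs a tie rule stated in advance. In the simulated scenarios about half of discharges up to Day 45 (50% and 52%) fell nearest to a day that already had a value. The Day 20 bias was −0.07 and −0.25 if the discharge score replaced that value, and −0.27 and −0.58 if it did not.

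RASS is a coarse ordinal scale and should be summarised descriptively or analysed by an ordinal method.

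The cost is wording only: same software, visits and data. There are two downsides. Earlier days come after less exercise. The model also assumes data are missing at random given observed function, so add a simple sensitivity analysis, for example the discharge score carried forward for early discharges and worst rank for deaths.

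### The chi-square test planned for nine discharge codes is too sparse at about 10 patients per group, and no favourable disposition is defined for Aim 3

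*Combined protocol and SAP*

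**What the plan says.** The Hospital Outcomes list under Data Collection for Aims 1-3 introduces the variable as "Discharge disposition- assigned a number for statistical analysis". It then gives nine codes. Code 1 is home. Codes 2 to 4 are home with some form of support: assistance, home therapy or outpatient therapy. Codes 5 to 8 are four kinds of facility, and code 9 is transfer to another hospital. Death in hospital has no code.

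Statistical Considerations restates Aim 3 as a directional claim: "Leg exercise on the Moveo will improve hospital outcomes". For this outcome the method is: "Discharge disposition, categorical data, will be analyzed via Chi-Square test".

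Research Design & Methods, like section 8.1 of the local protocol, plans 10 participants in each group and adds: "To account for attrition, 24 total subjects will be recruited; 12 per group". The documents do not merge codes, make them mutually exclusive, rank them, name a favourable result, or provide an exact test for small counts. They give no significance level or power, and no expected distribution of disposition.

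**The concern.** There are two separate problems.

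1. **Validity.** The chi-square p-value is a large-sample approximation, and 20 to 24 patients spread over up to 18 cells is far from large.
2. **Target.** The test asks whether the two groups differ in any way across unordered labels. Aim 3 asks whether disposition improves. A patient who goes home with assistance may also have home or outpatient therapy, and no rule says which code applies. A difference in how such patients are coded counts as much as a move from facility to home. A real move of that kind is diluted over several columns.

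At stake is one of the six hospital outcomes. A non-significant result could hide a sizeable shift, and a significant one might have nothing to do with getting patients home. Without a prespecified favourable outcome, any directional reading would be chosen after seeing the data.

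**Working it through.** **Inputs from the documents.** Nine codes; 10 per group evaluable, 12 recruited; Pearson chi-square.

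**Assumptions, because the documents give no figures.** Two-sided alpha of 0.05; the home rates; the spread of patients within the home codes and within the not-home codes. The plan has no power figure for this outcome to reproduce.

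**1. Expected counts.** The average over the 2 × 9 table is 20/18 = 1.1, or 24/18 = 1.3 at 12 per group. If only k codes are used, the average is 10/k, so it reaches the conventional 5 only when k = 2.

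**2. Type I error.** With 30% home in both arms and 10 per group, the nine-code chi-square rejected in 1.3-2.1% of simulated trials over three assumed spreads (3,000 runs each). Fisher's exact test on home versus not home rejected in 0.9-1.3%. Both are conservative, so the power difference in step 5 does not come from a looser test.

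**3. A shift the test can miss.** With equal arms the statistic is X² = Σ (a − b)²/(a + b) over the occupied codes.
- Group A, codes 1-5: 3, 2, 2, 2, 1 (9 of 10 home).
- Group B, codes 1, 4, 5, 6, 7, 8, 9: 1, 1, 2, 2, 2, 1, 1 (2 of 10 home).
- X² = 1 + 2 + 2 + 1/3 + 1/3 + 2 + 2 + 1 + 1 = 11.67 on 8 df (critical value 15.51), p = 0.17.
- Fisher's exact test on 9/10 versus 2/10: p = 0.005.

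This table is an extreme case, chosen to show the mechanism.

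**4. Significance with no shift.** Both arms send 7 of 10 home and use facilities identically (two codes, 2 and 1 patients). Six of the home patients are coded as home therapy in one arm and as home with assistance in the other. Then X² = 6²/6 + 6²/6 = 12 on 4 df, p = 0.017, with identical home rates.

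**5. Power for home 80% versus 30%, 10 per arm.** Separate runs differ by a point or two.

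| Spread within the home and not-home halves | Nine-code chi-square | Home/not-home Fisher |
|---|---|---|
| Even | 14% | 43% |
| 70% in one code per half | 28% | 42% |
| 85% in one code per half | 39% | 43% |
| All in one code per half (limiting case) | 63% | 42% |

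In the last row the table has collapsed to 2 × 2, so the chi-square is no longer a nine-code test. At 12 per arm, over the three spreads of step 2, power is 22-42% versus 59-62%. For home 90% versus 20% at 10 per arm it is 41% versus 83% with an even spread, and 77% versus 83% with 85% in one code.

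**6. What sample size alone explains.** For home 70% versus 30% at 10 per arm, the nine-code test has 9-21% power and Fisher 23-26%. For 80% power on two proportions, n per group = [1.96 √(2p̄(1 − p̄)) + 0.842 √(p₁(1 − p₁) + p₂(1 − p₂))]² / (p₁ − p₂)². For 30% versus 70% this is (1.386 + 0.545)²/0.16 = 23.3, so 24 per group. For 30% versus 60% it is 42.

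**The case against.** The strongest reply is that the loss rests on an assumed spread. That stands: an even spread is close to the worst case for the nine-code test. With 85% of patients in one code per half the two analyses are nearly level, and in the limit the order reverses. The loss can only be given as a range.

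Second, this is a pilot and N = 20 accounts for much of the low power. That also stands. Under Fisher's test, 8/10 versus 3/10 home gives only p = 0.07.

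Third, the home/not-home cut has a price. Suppose home is 20% in both arms and codes 6 and 7 hold 70% and 10% in one arm but 10% and 70% in the other. The planned test then has about 85% power and the dichotomy about 1%. An ordinal analysis would keep such information, but it needs a ranking that the documents do not supply, and codes 2 to 4 and code 9 have no evident order.

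Fourth, disposition is taken from the medical record, which may follow a coding convention. The documents do not describe one, so ambiguity is shown but arbitrary coding is not.

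A reader might also infer that the plan cannot show improvement at all. The documents do not support that. Direction can be read from the cross-table, and a two-sided Fisher p-value is just as unchanged when the arms are swapped. What is missing is a prespecified favourable outcome. Nor does the test miss every large shift: for home 10% versus 90% its power is 66-90% at 10 per arm.

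**Conclusion.** The concern holds in a limited form. The sparse-table problem follows from the plan's own numbers and needs no assumption about disposition: expected counts average 1.1 to 1.3, and no rule covers this. The approximation errs on the conservative side, with about 1-2% rejection under the null in the scenarios tried. The mismatch with Aim 3 also follows from the text, since a global test on unordered, partly overlapping codes does not address improvement and no favourable outcome is named.

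The power cost is conditional. For home 80% versus 30% at 10 per arm it is about 13-39% against about 42-44%, with little difference when most patients fall in one code per half. These figures rest on the assumed alpha, home rates and spreads. Neither analysis is well powered for moderate shifts, so the change makes the result valid and interpretable without making it decisive. The consequence is confined to one hospital outcome under the third aim of a pilot. The change should still be made, because it costs almost nothing.

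**What to change.** Replace the disposition sentence under Aim 3 with a prespecified binary outcome: discharged home (codes 1-4), the favourable result, versus not home (codes 5-9). State explicitly how code 9 and in-hospital death, which has no code, are counted. Compare the groups by Fisher's exact test, and report the difference in proportions with a confidence interval so that direction and uncertainty are both visible. Keep recording all nine codes and show them by group in a descriptive table.

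The cost is a sentence or two of analysis wording, settled before outcome data are examined, with no new data collection. The downside is that differences between types of facility, or between types of home service, are described and not tested.
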